2 ABSTRACT

This is a randomized controlled trial to test a combination behavioral and biomedical interventions to improve the HIV prevention and care cascades in a population of mobile men in a high priority setting (fishermen in Kenya). The intervention strategy is to recruit and train highly socially-connected men to distribute HIV self-tests and provide linkage support to men in their close social networks. The study will determine whether this social network-based approach along with small financial incentives in the form of transport vouchers can increase men's self-testing, linkage to and uptake of ART and PrEP after self-testing, virologic suppression at 6 months (for those initiating ART) and PrEP adherence (for those initiating PrEP) at 6 months. The study includes a longitudinal qualitative and mixed methods (quantitative and qualitative assessments) to identify the pathways of intervention action, and understand how the social network-based approach with support for linkage affects testing and ART and PrEP uptake and retention in men.

3 PROTOCOL SUMMARY

3.1 SYNOPSIS

Title:	Self-Test Strategies and Linkage Incentives to Improve ART and PrEP Uptake in Men			
Grant Number:	1R01 MH120176			
Brief Summary:	This is a randomized controlled trial to test a combination behavioral and biomedical intervention to improve the HIV prevention and care cascades in a population of mobile men in a high priority setting (fishermen in Kenya). The intervention strategy is to recruit and train highly socially-connected men to distribute HIV self-tests and provide linkage support to men in their close social networks. The study will determine whether this social network-based approach along with small financial incentives in the form of transport vouchers and biomedical technologies can increase men's HIV testing (within3 months linkage to and uptake of ART and PrEP after testing (within 3 months, and virologic suppression (HIV RNA < 400 c/mL) at 6 months and PrEP adherence (tenofovir levels of >=1500 ng/mL in urine) at 6 months. The study includes a longitudinal qualitative and mixed methods quantitative and qualitative assessments to identify the pathways of intervention action, and understand how the social network-based approach with support for linkage affects testing and ART and PrEP uptake and retention in men.			
Study Design:	Cluster randomized controlled trial of a combination intervention to increase men's HIV testing uptake, increase their linkage to and uptake of ART and PrEP, and improve their outcomes (virologic suppression for HIV-infected men and adherence to PrEP in uninfected men)			
Study Population:	At least 650 and up to 1,800 men aged ≥18 years who are primarily working in the fishing industry or related activities, who reside in beach communities in Siaya. Study population will consist of up to 140 clusters of men with close social network ties with a variable number of men in each cluster.			
Description of Sites/Facilities Enrolling Participants:	 Clinic sites: up to 10 beach landing sites and associated clinics, within one or more sub-counties, Rarieda, Bondo and Alego Usonga, in Siaya County in western Kenya Community sites: up to 10 Lake Victoria beach communities (with Beach Management Unit -governed landing sites) within sublocations in Rarieda, Bondo and/or Alego Usonga 			
Objectives:	 Determine whether providing training and HIVST to select fishermen to distribute to other men in their close social networks increases men's HIV testing uptake; Determine whether network-central promoters and small incentives can improve ART and PrEP uptake among men in their close social networks; and Test the impact of interventions on ART or PrEP retention and adherence. 			
Approach:	In Aim 1, following the study pilot, community selection, and preparation (see 'recruitment and retention plan') the study team will conduct a census/BMU registry verification in study communities to identify the population of men eligible for the study. We will screen, recruit and enroll eligible men who give their informed consent to participate, then measure their close social networks identify network-central, highly-connected men ("promoters") and randomize their close social network (a cluster) to 1:1 intervention and control groups. We will then			

	conduct a baseline survey to collect sociodemographic and baseline sexual behavior data among men in the close social networks. Following this baseline data collection, all promoters will be provided a training. Promoters in the intervention group will receive HIVST training, multiple HIVST for distribution to other men, and a small amount of remuneration. Promoters in the control group will receive basic HIV ducation and training about the study, and will be given vouchers that can be exchanged for HIV tests (standard or free HIVST kits) at nearby health facilities. Using follow-up survey data, we will test the hypothesis that a higher rate of HIV testing will be observed after 3 months among men in networks that receive the intervention compared to control.
Description of Study Intervention:	periods corresponding to the timing of quantitative outcome measurements in Aims 1 through 3. Intervention type: Behavioral intervention trial The intervention strategy is to recruit and train highly socially-connected men to distribute HIVST and provide linkage support (encouragement, along with small
intervention:	distribute mixs) and provide linkage support (encouragement, along with small

Study Duration Participant Duration:	5 Years Approximately 30 months
Outcome Measures:	 Primary outcomes Self-reported HIV testing within 3 months of intervention start Linkage to care or prevention within 3 months of intervention start Viral suppression (HIV RNA <400 c/mL) at 6 and 12 months among HIV-positive participants PrEP adherence at 6 months Secondary outcomes Initiation of ART or PrEP within 3 months confirmatory test or PrEP eligibility screening Confirmatory HIV testing uptake 3 to 6 months after intervention start
	financial incentives to offset transport costs) to other men in their close social network.

Self-Test Strategies and Linkage Incentives to Improve ART and PrEP Uptake in MenVersion 11.0November 29, 2022

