5 OBJECTIVES AND ENDPOINTS

Table 2. Overview of Study Aims, Design, and Outcomes

	Study design and interventions	Outcomes
--	--------------------------------	----------

Aim 1	 Self-reported HIV testing within 3 months of intervention start BMU census / registry verification & updating Baseline social network data collection Identification of close social networks and network-central 'promoters' Baseline survey among those randomized to control and intervention RCT: Intervention: Promoters given training & multiple STs, & asked to offer STs to men in their social networks. Control: Promoters given basic training & vouchers for HIV testing (including HIVST) at clinics to offer to men in their networks 3-month follow-up survey Measure impact of intervention on linkage to & uptake of ART & PrEP Intervention: Promoters are given incentives (clinic transport reimbursement vouchers valued at ~\$5) & encouraged to give to men in their networks to promote linkage to ART or PrEP 	 Self-reported HIV testing uptake within 3 months Confirmatory HIV testing uptake 3 – 6 months after intervention start Linkage to ART or to PrEP within 3 months after self-reported HIV testing Initiation of ART or PrEP (among those eligible), within 3 months of confirmatory testing (linkage)
	 after HIV testing 2. Control: Promoters given same training & info, but no linkage incentives 	
Aim 3	 Measure impact of intervention on ART & PrEP retention & adherence Men who test HIV-positive undertake VL testing and counseling at scheduled intervals to ascertain adherence to ART Men who test HIV pagative 	 Viral suppression (HIV RNA <400 c/mL) and adherence at 6 & 12 months Adherence to PrEP (TFV levels of >=1500
	 Men who test HIV-negative undertake rapid HIV & TFV testing with counseling at scheduled intervals and urine testing to ascertain PrEP adherence 	ng/mL in urine = adequate adherence ²⁸) at 6 months
Qualitative	Across all aims, we will assess the path mixed methods quantitative and qualit	ways of intervention action using qualitative and ative assessment. We will identify the

Studies	mechanisms of action, and barriers and facilitators of the social network and incentives
	intervention implementation, using qualitative and mixed methods quantitative and
	qualitative assessments embedded in Aims 1, 2 and 3. The data collection approach will
	include in-depth interviews with participants in both groups, key informant interviews

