Follow up surveys will be conducted with study participants at 3 months. Please note that at this stage of the data collection, there will be three possible study participants groups for which we will provide individualized surveys, (1) those who were mapped during the social network mapping exercise and identified as a part of the network where the central promoter was randomized to control or intervention, (2) those who were not mapped or named during the baseline social network mapping exercise but received an HIVST with an incentive voucher (intervention) or referral voucher (control) from a central promoter, and (3) central promoters themselves. These surveys will assess self-reported HIV testing among study participants, whether they sought confirmatory testing, whether they linked to ART or PrEP, interactions they had with study promoters, as well as assess health behaviors. We will have three versions of the follow up survey which are attached to this protocol.

8.7 BIOSPECIMEN COLLECTION AND CLINICAL DATA TO ASSESS CONFIRMATORY TESTING, LINKAGE TO ART AND PREP, AND LONG TERM OUTCOMES

*Up to n=1500 participants**

* We do not know aprior the rate of care or prevention uptake so the total numbers are tentative.

Visit 2 (for 6 months) for new participants (those not mapped in the baseline but received self-tests with incentive vouchers (intervention) or referral vouchers (control) from promoters and then linked to care or prevention

Visit 4 (for 6 months) for baseline mapped and surveyed participants who received self-tests with incentive vouchers (intervention) or referral vouchers (control) from promoters and then linked to care or prevention

Visit 5 (for 6 months) for promoters who will have participated in the social network survey, baseline survey, and promoter trainings (visits 1 2 and 3, respectively) and then linked to care or prevention

We will obtain informed consent in clinics, from all of the study participants who opt to visit a study clinic for confirmatory testing, for the release of medical record data. The clinical data abstraction and follow

up bio-specimen collection will take place for two cohorts (1) those who HIV test, link to care and are enrolled in care and taking ARVs, and (2) those who HIV test, are HIV-negative, screened and eligible for and start PrEP. The chart abstraction data focused on 6-month outcomes will be collected retrospectively through the end of year 4, June 2023.

HIV-positive study participants

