For those who are identified as HIV-positive through abstraction of medical records from the MOH data where the study is being implemented, the study will also conduct viral load measurements utilizing venous blood draw a during study visit at 6 months following intervention start. Participants will also participate in a brief survey to assess adherence to ART at the 3 and 6 month timepoints. Participants will be consented and asked to have their blood drawn by a trained phlebotomist/lab technician for measurement of viral load. Collection of blood for testing of HIV viral load at 6 months since the start of the intervention (note that the MOH program includes annual VL testing, which the study will supplement with additional testing to ensure study measurements). Phlebotomy will be performed using universal precautions, and specimens will be aliquoted, assigned a unique number, and stored at -70 C until shipment to laboratory for processing. Viral load testing will be performed on venous blood on Abbott realTime HIV-1 platform and assay, with a detectable threshold of 40 cells per microlitre. The venous sample and results of the viral load test will only be released to the study and not the MOH facility or those providing the patient's care. As a result, the measurements will majorly be for outcome measurements related to the trial. If requested by providers to make care decisions, and with the verbal consent of the study participant, we may share the results of the viral load in an effort to improve the care of patients and to fulfill our ethical obligations. Further, results or information will be shared with the participants if requested. Participants, through the consent forms, will be advised of the study purposes for the venous blood draw and that the results may be shared with them, if they request, or with their healthcare providers if requested and provided we have the patient's verbal consent.

HIV-negative study participants

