1 STATISTICAL CONSIDERATIONS

1.1 STATISTICAL HYPOTHESES

Primary Endpoint(s): self-reported HIV testing in the past 3 months by participants, as measured in the 3-month follow-up surveys.

We hypothesize that the intervention group will be more likely to test for HIV than the control group.

Primary Endpoint (s): Linkage to ART or to PrEP within about 3 months and Initiation of ART or PrEP (among those eligible), within 3 months of linkage

We hypothesize higher a proportion of participants linking to ART or PrEP (confirmatory testing and ART referral for positives, and PrEP screening for negatives among those receiving the intervention. We also hypothesize higher ART and PrEP uptake within 3 months among men in social networks assigned to the intervention group.

Primary Endpoint (s): Viral suppression (HIV RNA <400 c/mL) at 6 months and adherence to PrEP (TFV levels of >= 1500 ng/mL in urine = adequate adherence 28) at 6 months.

We hypothesize a higher proportion of individuals both retained in care and adherent to treatment in the intervention group compared to the control group.

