Analytic Plan: For the test of the *social network-central promoters and small incentive* intervention effect on the primary outcome of linkage to care or prevention within 3 months of intervention start we will utilize a cluster adjusted Pearson's Chi-square test comparing the proportion of subjects with documented linkage to care or prevention in the intervention versus the control arm. In secondary analysis, we will utilize multilevel mixed-effects logistic regression as described in Aim 1 to investigate factors that influence the probability of success of linkage to care and prevention. We will also evaluate the secondary outcomes of ART initiation among HIV-positive persons not currently on treatment, and initiation of PrEP among HIV-negative persons who screen as eligible. We will compare the initiation proportions between study arms using cluster adjusted Chi-square tests and additional multilevel mixed-effects logistic regression to identify influencing factors.

We will measure the combined outcome of 1) Proportion of HIV-positive participants with viral suppression (HIV RNA <400 c/mL) at 6 months missing=failure (unsuppressed) and 2) Proportion of participants adherent to PrEP (TFV levels of >=1500 ng/mL in urine indicating adequate adherence) at 6

months missing=failure (nonadherent). PrEP adherence will be measured at 6 and 12 months after initiation using our novel technology of *point-of-care rapid testing to assess TFV adherence in urine*). (+ about 1 month for all measures)

Secondary Outcomes: HIV testing uptake 3 to 6 months after intervention start and retention on ART at 6 months or PrEP at 6 months. Using clinic records, we will assess whether men had confirmatory HIV testing and those who initiated PrEP and ART attended scheduled appointments and record VL results. (+ about 1 month for all measures)

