## Section 6: Analysis

# 26) Outcome definitions

- a. Primary Outcomes:
  - i. Proportion of HIV testing: The first primary outcome will be the proportion of study participants who self-report HIV testing in the last three months (at the 3 month follow up visit) compared to those who self-report not using testing during the last three months.
  - ii. Proportion of HIV self-testing: The second outcome will be the proportion of study participants who self-report using the self-testing kit in the last three months (at the 3 month follow up visit) compared to those who self-report not using a self-testing kit during the last three months.
  - iii. Proportion with successful linkage to ART or PrEP within 3 months of intervention start (ie: when promoters receive self-test kits to distribute). The second primary outcome will be defined as the proportion of individuals who link to ART (if confirmatory HIV testing is positive) or PrEP evaluation (if confirmatory HIV testing is negative), meaning they present at a study facility/clinic (depending on results of HIV testing) within three months of the intervention start (defined as from when study promotors receive the kits for distribution).
  - iv. HIV treatment and prevention success: The third primary outcome is a composite measure meant to capture "success" in HIV prevention and/or treatment behaviors (ie: Viral suppression among HIV+ and adequate TFV among those prescribed PrEP). The measure will be defined as either adequate levels of tenofovir, indicating PrEP adherence (defined as TFV levels of <1500 ng/mL in urine indicating inadequate adherence vs. ≥ 1500 ng/ml) among HIV seronegative individuals who screened eligible for PrEP *or* the proportion of HIV-positive participants with viral suppression (defined as HIV RNA <400 c/mL using the Abbott realTime HIV-1 platform and assay, with a detectable threshold of 40 cells per microlitre) at 6 and 12 months. Secondary thresholds of <1000 copies/mL will also be examined. PrEP adherence will be measured at 6 and 12 months after initiation using our novel technology of *point-of-care rapid testing to assess TFV adherence in urine* (developed by Co-I [name] in collaboration with Alere Rapid Diagnostics™). For both components of the measure, we will define missing values as failure (i.e. inadequate adherence or unsuppressed).

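### Protocol version 11.0 still names 12-month viral suppression and PrEP adherence as outcomes but schedules no study measurement of either after month 6

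*Protocol*

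**What the plan says.** **Where month 12 survives in the protocol.** The synopsis (section 3.1) lists "Viral suppression (HIV RNA <400 c/mL) at 6 and 12 months among HIV-positive participants" as a primary outcome, and next to it "PrEP adherence at 6 months". Table 2 in section 5 gives the Aim 3 outcome as "Viral suppression (HIV RNA <400 c/mL) and adherence at 6 & 12 months". Section 1.3.3 states that "PrEP adherence will be measured at 6 and 12 months after initiation". Appendix item 6.1.11 still lists an adherence tool for 6 and 12 months.

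**Where the protocol stops at month 6.** The procedures in section 8.7 provide for "Collection of blood for testing of HIV viral load at 6 months since the start of the intervention" and place the urine assay at the 6-month visit. On records, the same section says: "The chart abstraction data focused on 6-month outcomes will be collected retrospectively through the end of year 4". Table 1 (section 3.2) has one mark each for viral load and urine tenofovir, which reads as the 6-month column. Table 5 (section 8.11) pays for a 6-month specimen visit only, and section 6.10 defines completion by the 6-month assessments. The hypotheses in section 1.1 name "Viral suppression (HIV RNA <400 c/mL) at 6 months and adherence to PrEP", also at 6 months. The composite definition in section 1.3.3 and the retention outcome in sections 1.2 and 1.3.3 are at 6 months.

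**The SAP.** Section 3 ties it to Protocol 4.0 of May 2020. Section 15 plans data collection at 0, 3, 6 and 12 months. Section 26.a.iv sets the composite "at 6 and 12 months. Secondary thresholds of <1000 copies/mL will also be examined" and, in the same item, counts missing values as failures. Section 28 applies that rule to primary outcomes under intent to treat. Sections 11 and 27.c put retention at 12 months.

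**The concern.** A primary outcome is named at a time when the current procedures collect no study specimen for it. An analyst holding both documents faces two problems.

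- **What the 12-month value would be.** Under the SAP's rule, a man with no 12-month measurement counts as a failure. A 12-month composite would then mostly record that nothing was measured, not whether men were suppressed or adherent.
- **Which time point carries the Aim 3 test.** The current protocol's hypotheses and composite say month 6. The synopsis and the SAP say months 6 and 12. Neither document says how the two would be combined or ranked, and SAP section 17 makes no multiplicity adjustment. That leaves room to choose the time point after results are seen.

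**Working it through.** **Inputs** (protocol section 1.2, Aim 3, unless stated)
- Expected men: 168 on PrEP + 72 on ART = 240.
- Success: 70% control, 89% intervention. Design effect 1.7.
- Two-sided 5% level (SAP section 16).
- 1:1 allocation by network (section 6.5), taken here as 120 men per arm with the same ART/PrEP mix in each (assumption).

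**Formula.** With effective n per arm and p̄ the mean of p1 and p2:

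power = Φ{[(p2 − p1) − 1.96·√(2p̄(1 − p̄)/n)] / √[(p1(1 − p1) + p2(1 − p2))/n]}

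**Step 1: reproduce the plan's month-6 figure.**
- n = 120/1.7 = 70.6.
- p1 = 0.70, p2 = 0.89, p̄ = 0.795.
- Numerator: 0.19 − 1.96 × 0.0680 = 0.0568. Denominator: 0.0660.
- Φ(0.86) = 80.5%, matching the stated 80% or more.

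**Step 2: the 12-month composite under version 11.0 procedures and the SAP rule.** No 12-month urine test is scheduled, so all 168 PrEP men (168/240 = 70%) are failures. Let f be the share of the 72 ART men with a routine viral load near month 12. The documents give no f, so a range is shown. Applying the plan's 70% and 89% to these men (assumption):

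success = rate × f × 72/240

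| f | Control | Intervention | Power |
|---|---|---|---|
| 0 | 0% | 0% | undefined |
| 0.25 | 5.25% | 6.7% | 5% |
| 0.5 | 10.5% | 13.4% | 8% |
| 0.75 | 15.75% | 20.0% | 10% |
| 1 | 21.0% | 26.7% | 12% |

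For f = 1: 0.70 × 0.30 = 0.21 and 0.89 × 0.30 = 0.267. Then (0.057 − 1.96 × 0.0717)/0.0716 = −1.17, and Φ(−1.17) = 12%.

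**Step 3: sensitivity to the design effect.** With no clustering at all (n = 120) and f = 1: (0.057 − 1.96 × 0.0550)/0.0549 = −0.93, so power is about 18%.

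**Step 4: viral suppression alone.** The synopsis names only this component at month 12. Taking the 72 ART men, 36 per arm, effective n = 36/1.7 = 21.2. Power is 6%, 9% and 33% at f = 0.25, 0.5 and 1. With design effect 1 and f = 1 it is 52%.

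**The case against.** The strongest reply has four parts.

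1. **No single document produces the harm.** In protocol section 1.3.3 the missing = failure rule is attached to month 6. Only the SAP carries it to month 12, and that SAP plans 12-month visits. This is correct. The damage arises only when the SAP is applied to the version 11.0 procedures. But these are the plans on hand, and the SAP's revision list records no update from Protocol 4.0.

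2. **Some 12-month viral loads may exist.** Section 8.7 notes annual viral load testing in the Ministry of Health programme, section 1.3.3 records viral loads from clinic files, and SAP section 9 speaks of routine viral load testing. This also stands. A reader might infer that every man would be scored a failure, giving 0% versus 0%. The documents do not support that: it is only the limiting case f = 0. What is missing is a 12-month window and an abstraction rule, and abstraction is focused on month 6.

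3. **The synopsis puts only viral suppression at month 12.** True, so the 240-man composite at 12 months comes from the SAP. Step 4 gives the narrower outcome, which is also underpowered.

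4. **The current composite is clear.** Sections 1.1, 1.2 and 1.3.3 all use month 6, and the stated power reproduces. That stands; the sample-size basis is not in question. A reader might also suppose that success needs both time points, which would reduce the whole composite to failures among PrEP men. Nothing in either document requires both.

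**Conclusion.** The conflict is real and lies inside the current protocol: month 12 survives in the synopsis, Table 2, section 1.3.3 and the appendix list, while the procedures, payment, completion definition and hypotheses stop at month 6. The finding does not depend on reading a broken schedule table, because sections 6.10, 8.7 and 8.11 say the same in words.

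Applying the SAP's composite and missing-data rule to version 11.0 would make 70% of the expected men automatic failures at month 12. Composite success would then be at most about 21% versus 27%, with about 12% power, against 70% versus 89% and 80.5% at month 6. These bounds assume equal arms with the same ART/PrEP mix, the plan's success rates holding among ART men at month 12, and a routine result for all 72 of them. A lower share gives less. The month-6 analysis is unaffected.

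**What to change.** Make month 6 the single Aim 3 primary time point.

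- **Protocol:** remove month 12 for viral suppression and PrEP adherence from the synopsis, Table 2, section 1.3.3 and appendix item 6.1.11. Retention needs no change; it is already at 6 months.
- **SAP:** remove month 12 for viral suppression, PrEP adherence and retention from sections 8c, 9, 11, 15, 26.a.iv, 26.b and 27.c, and update the protocol version it cites.
- **Missing data:** state that missing = failure applies only to scheduled measurements. Report any routine 12-month viral loads descriptively.
- **Time origin:** do not move the PrEP anchor silently. Section 1.3.3 counts PrEP adherence from initiation, section 8.7 counts viral load from intervention start, and SAP section 9 starts the timeline at enrolment and the baseline interview. Reconcile these openly.

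If the team wants to keep month 12, it must instead state a data source, a window and the role of that time point.

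The cost is an amendment of wording with no scheduled measurement lost. It does remove a named primary time point, so the reason should be documented before outcome data by arm are examined. The trial gives up a 12-month primary claim for which it has no scheduled measurement.

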1.3.3 ANALYSIS OF ADDITIONAL ENDPOINT(S)

Primary Outcome: the primary outcome measure will be linkage to care or prevention within 3 months of the Aim 1 intervention start. Linkage will be defined for HIV-positive participants as a documented confirmatory HIV test result, and a documented HIV clinic visit following referral. Linkage will be defined for HIV-negative participants as documented evidence of evaluation for PrEP (following standard of care procedures) extracted from medical records.

Secondary outcome: The secondary outcomes will be confirmatory HIV testing uptake 3 – 6 months after intervention start and the initiation of ART, or PrEP (among those screened as eligible), within 3 months of the confirmatory test or eligibility screening. HIV testing uptake will be measured via documented testing records in clinic records and ART start will be measured via documented prescription for ARV medications, and for PrEP start, via oral PrEP prescription.

Third outcome: The third primary outcome is a composite measure meant to capture "success" in HIV prevention and/or treatment behaviors. The measure will be defined as either adequate levels of tenofovir, indicating PrEP adherence (defined as TFV levels of >= 1500 ng/mL in urine indicating adequate adherence vs. < 1500 ng/ml) among HIV seronegative individuals who screened eligible for PrEP or the proportion of HIV-positive participants with viral suppression (defined as HIV RNA <400 c/mL using the Abbott realTime HIV-1 platform and assay, with a detectable threshold of 40 cells per microliter at 6 months. PrEP adherence will be measured at 6 months after initiation using our novel technology of point-of-care rapid testing to assess TFV adherence in urine (developed by Co-I [name] in collaboration with Alere Rapid Diagnostics[™]). For both components of the measure, we will define missing values as failure (i.e. inadequate adherence or unsuppressed).

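### As worded, the secondary confirmatory-testing outcome leaves out tests in months 0 to 3, so it understates, and under some assumptions reverses, the effect on confirmatory testing.

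*Protocol*

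**What the plan says.** The Protocol gives the same window in four places. The Synopsis (3.1) lists "Confirmatory HIV testing uptake 3 to 6 months after intervention start" as a secondary outcome. Table 2 (section 5) has "Confirmatory HIV testing uptake 3 – 6 months after intervention start". Section 1.3.3 states "The secondary outcomes will be confirmatory HIV testing uptake 3 – 6 months after intervention start" and later lists "HIV testing uptake 3 to 6 months after intervention start and retention on ART at 6 months or PrEP at 6 months". That last wording drops the word confirmatory, but the sentence after it restores it. No section gives a version that runs from intervention start. None gives a denominator, or a rule for a man who confirmed before month 3.

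The neighbouring primary outcome covers the earlier period: "the primary outcome measure will be linkage to care or prevention within 3 months of the Aim 1 intervention start". For HIV-positive men it requires "a documented confirmatory HIV test result, and a documented HIV clinic visit following referral". For HIV-negative men the Protocol asks only for "Linkage will be defined for HIV-negative participants as documented evidence of evaluation for PrEP". SAP 26.a.iii goes further and ties the PrEP route to a negative confirmatory test.

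The voucher in Protocol 8.5, given only in the intervention arm, reimburses men who come for confirmatory testing and for ART or PrEP screening within three months of self-testing. Kits and vouchers are marked from baseline in Table 1 (3.2). The secondary outcomes in SAP 26.b do not include confirmatory testing.

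**The concern.** The intervention is designed to bring men to the clinic soon after a self-test. An HIV-positive man who succeeds on the primary linkage outcome has a confirmatory test on record by month 3, normally before the secondary window opens. Read literally, the secondary outcome does not credit that test. If the intervention works as hoped, more early tests go uncounted in the intervention arm than in control, and fewer men there are left to test for the first time later.

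The result could be a secondary analysis that shows little effect, or one in the opposite direction to the primary linkage result, without any failure of the intervention. Two analysts could also report different signs, depending on whether they read the window literally or as everything up to month 6.

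**Working it through.** **Nearest stated figure.** The documents give no rates or power for confirmatory testing. The closest is Aim 2 linkage: 24% control and 39% intervention, ICC 0.15, two-sided 5% (Protocol 1.2; SAP 11 and 16).

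- Odds ratio: (0.39/0.61) / (0.24/0.76) = 2.02, matching the stated 2.0.
- SAP inputs, 40 clusters of 8 per arm: design effect 1 + 7 × 0.15 = 2.05; 320/2.05 = 156 effective men per arm; power 81.7%, matching the stated 80% or greater.
- Protocol inputs, 70 clusters of 7 per arm: design effect 1 + 6 × 0.15 = 1.90; 490/1.90 = 258 per arm; power 95.8%, consistent with 80% or greater.

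**Assumptions for the illustration.** The 24% and 39% stand in for the share confirmed by month 3. Each man's first confirmatory test is counted once. The late rate h is the share of men not confirmed by month 3 who confirm in months 3 to 6. It is not in the documents, so a range of 5% to 39% is shown.

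**Formulas.**

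- Window outcome = (1 − share confirmed by month 3) × h, so 0.76h in control and 0.61h in intervention.
- Cumulative outcome = share confirmed by month 3 + window outcome.
- With equal h, the window difference is (0.61 − 0.76)h = −0.15h and the window ratio is 0.61/0.76 = 0.80, whatever h is.
- With equal h, the cumulative difference is 0.15 − 0.15h.

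| h, both arms | Window, control | Window, intervention | Window difference | Cumulative, control | Cumulative, intervention | Cumulative difference |
|---|---|---|---|---|---|---|
| 5% | 3.80% | 3.05% | −0.75 | 27.80% | 42.05% | +14.25 |
| 24% | 18.24% | 14.64% | −3.60 | 42.24% | 53.64% | +11.40 |
| 39% | 29.64% | 23.79% | −5.85 | 53.64% | 62.79% | +9.15 |

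**Unequal late rates.** The window difference is zero when h in the intervention arm is 0.76/0.61 = 1.25 times h in control. With control at 24%, the intervention arm needs about 29.9%. At 39% against 24%, the window gives 0.61 × 0.39 − 0.76 × 0.24 = 23.79% − 18.24% = +5.55 points. The cumulative difference is then 62.79% − 42.24% = +20.55 points.

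**What does not depend on h.** When first tests are counted, the cumulative difference equals the month-3 difference plus the window difference. With the stand-in rates, the window therefore falls short of the six-month effect by 15 points for any pair of late rates. Only the sign depends on h.

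**The case against.** **The window may have been meant as by month 6.** The 3-month survey asks about confirmatory testing (8.6). Table 1 marks linkage at the 6-month column although linkage is a three-month outcome. A self-test by month 3 followed by a three-month voucher also reaches month 6. This reading is possible, but no section states it, and the same Synopsis list words other outcomes as within three months. If it was the intent, the definition still has to say so.

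**The sign is not established.** This stands. Kits and vouchers are still marked at the 3-month column and promoter support at the 6-month column, so the intervention also acts inside the window. A reader might infer that an effective intervention will look harmful; the documents do not support that. The first-test rule is also an assumption. Table 2 has HIV-negative men retested at scheduled intervals, and counting those repeats could favour the arm that links faster.

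**The inputs are borrowed.** This stands too. The 24% and 39% combine ART and PrEP linkage, and the Protocol requires a confirmatory test for linkage only in HIV-positive men; the extension to HIV-negative men rests on the SAP. If only undiagnosed HIV-positive men matter, and the 10% undiagnosed figure for adults in section 4.2 is assumed to apply, 490 men per arm give about 49. A 3.6-point difference is then about two men. For this reason no probability of a statistically significant reversal is claimed.

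**It conditions on late testing.** A reader might also say that the window restricts the analysis to men who had not confirmed early. It does not: counted over all men, it leaves early events out of the numerator. Restricting the denominator to men untested at month 3 would be a different choice, and would compare groups selected after randomisation.

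**Conclusion.** The point holds as a defect in the definition of one secondary outcome. Taken as written, the window misses confirmatory tests in the period when linkage requires them for HIV-positive men and when the voucher pays for them. It therefore understates the six-month effect by whatever difference has built up by month 3. That is 15 points if the plan's linkage rates are used as stand-ins and first tests are counted. Reversal of sign is illustrative: it follows if late rates are equal, and fails once the intervention arm's late rate is more than about 1.25 times control's.

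A reader might infer that the linkage finding is compromised. It is not: primary linkage counts months 0 to 3 directly, and no primary outcome changes. The matter should still be corrected, because the SAP neither lists the outcome nor resolves the window.

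**What to change.** Redefine the outcome as the first documented confirmatory HIV test from intervention start to month 6 (+ about 1 month). Count each man once and compare by randomised arm. The denominator should be all men in randomised networks who were not known to be HIV-positive or on ART at baseline, so that it is fixed by baseline status and not by testing status at month 3. SAP 25 already lists baseline HIV and ART status.

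State that repeat tests do not count again. State also whether a clinic test in a man with a negative self-test counts as confirmatory, since the Protocol and SAP differ on its role in linkage. Tests in months 3 to 6 alone may be reported descriptively.

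Amend the Synopsis, Table 2 and both places in Protocol 1.3.3, and add the outcome to SAP 26.b. The cost is wording and a small amount of extra analysis. Testing is already taken from clinic records, and the 6-month chart abstraction is retrospective, so no new data source is needed.
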